13.1 Good Clinical Practice

The study will be conducted in accordance with the appropriate regulatory requirement(s). Essential clinical documents will be maintained to demonstrate the validity of the study and the integrity of the data collected. Master files should be established at the beginning of the study, maintained for the duration of the study and retained according to the appropriate regulations.

13.2 Ethical Considerations

The study will be conducted in accordance with ethical principles founded in the Declaration of Helsinki. The IRB will review all appropriate study documentation in order to safeguard the rights, safety and well-being of the patients. The study will only be conducted at sites where IRB approval has been obtained. The protocol, informed consent, written information given to the patients, safety updates, annual progress reports, and any revisions to these documents will be provided to the IRB by the investigator.

Appendix I - Eligibility Checklist A pilot study of activated charcoal in healthy volunteers

·	ticipant ID 19014-UMN (assigned in OnCore)		
	LUSION CRITERIA NO" response to any of the following disqualifies the participant from study entry.		
	 	Yes	No
1	Age ≥18 years		
2	No use of prescription medications, including oral birth control, currently or in the last 30 days		
3	Sexually active women must be using an effective form of contraception. Note that subjects who are on oral contraception should use an additional form of contraception such as barrier methods, as AC may interfere with the efficacy of oral contraceptive.		
4	Voluntary written consent signed before performance of any study-related procedure		
	CLUSION CRITERION YES" response to the following disqualifies the participant from study entry.	Yes	No
1	At risk of GI hemorrhage or perforation due to underlying pathology, recent surgery, or medical conditions that could be adversely affected by the administration of AC.		
2.	Planning to have an endoscopic procedure		
3.	Known hypersensitivity to AC		
4.	Non-English speakers		
Hav	e consent form signed: ing obtained consent and reviewed each of the inclusion/exclusion criteria, I verify that thiticipant is eligible.	is	
Sign	nature of person verifying eligibility Date		

Appendix II – Volunteer Product Rating Form

Study	ID:
Date:	
1.	Please rate your charcoal experience today by choosing one the 5 items below
	1 2 3 4 5
2.	Have you had any issues since last drink of charcoal that you think may be related to your charcoal experience?

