6.2 Subject Monitoring

Healthy volunteers will be observed for fifteen minutes after consuming the AC. Upon leaving the research unit, they will have access to the CRA via phone. For 2 days after each round of study product consumption, a member of the study team will contact the subject and screen for all grade 2 or higher AEs and SAEs.

Subjects with an adverse event will be followed until the event has resolved or stabilized with sequelae.

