6.6 Withdrawal from Study

Participants have the right to withdraw consent at any time by informing a member of the study staff or by following the instructions provided in the HIPAA document.

7 Schedule of Activities

	Screening Visit	Week 1-2
Consent and eligibility screening	Х	
Physical Exam	Х	
Drink Study product in either tap water, protein shake, or apple juice (per table 1*)		M, T, W
Rate Experience (taste test)		M, T, W
Screen for AEs		M, T, W
Telephone call from study staff to check for AEs		Th, F

8 Study Product Information

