8.1.7 Toxicities

GI Effects

May cause vomiting, constipation, diarrhea, and GI obstruction or fecal impaction in dehydrated patients.

Generally should not be used when decreased peristalsis present (reduced or absent bowel sounds); if risk of GI obstruction, perforation, or hemorrhage exists; if surgery has occurred recently; or if electrolyte imbalance or volume depletion exists.

Pulmonary Effects

Aspiration of activated charcoal may lead to more severe complications than aspiration of gastric contents alone. Aspiration from vomiting or misdirected nasogastric catheter has resulted in granulomatous reactions, bronchiolitis obliterans, tissue reaction to suspension agents (sorbitol, povidone), increased lung permeability, and rarely, death.

Use of Fixed Combination

When used in fixed combination with other agents, consider the cautions, precautions, and contraindications associated with the concomitant agents.

Common Adverse Effects

Vomiting, diarrhea, constipation, black stools.

9 Event Monitoring, Documentation and Reporting

Toxicity and adverse events will be classified and graded according to NCI's Common Terminology Criteria for Adverse Events version 5.0 (CTCAE V5) and reported on the schedule

below. A copy of the CTCAE can be downloaded from the CTEP home page. (http://ctep.cancer.gov/protocolDevelopment/electronic applications/ctc.htm#ctc 50).

The following definitions of adverse events (AEs) and serious adverse events (SAEs) will determine whether the event requires expedited reporting via the SAE Report Form in addition to routine documentation in the OnCore AE case report form (CRF).

Note: throughout this section the generic term "study drug" refers to study product, medical grade Oral AC.

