9.1 Event Terminology

Adverse Event: Any untoward medical occurrence associated with the use of a drug in humans, whether or not considered drug related.

Serious Adverse Event: An adverse event is considered "serious" if, in the view of either the investigator or sponsor, it results in any of the following outcomes:

- Death
- A life-threatening adverse experience
- Inpatient hospitalization or prolongation of existing hospitalization
- A persistent or significant incapacity or substantial disruption of the ability to conduct normal life functions
- A congenital anomaly/birth defect
- Important medical events that may not result in death, be life-threatening, or require hospitalization may be considered serious when, based upon appropriate medical judgment, they may jeopardize the patient or subject and may require medical or surgical intervention to prevent one of the outcomes listed in this definition.

Unexpected Event: An adverse event or suspected adverse reaction is considered "unexpected" if it is not listed in protocol-related documents (e.g. protocol, consent documents, investigator brochure, package insert), or is not listed at the specificity or severity that has been observed or given the characteristics of the subject population being studied.

Attribution: is the relationship between an adverse event or serious adverse event and the study drug. Attribution is assigned as follows:

- Definite The AE is clearly related to the study drug
- Probable The AE is likely related to the study drug
- Possible The AE may be related to the study drug
- Unlikely The AE is doubtfully related to the study drug

• Unrelated – The AE is clearly not related to the study drug Attribution must be assigned by the treating physician or the PI.

The following definitions are from the Masonic Cancer Center's Standard Operating Procedure (SOP) Deviation Reporting:

Major Deviation: A deviation or violation that impacts the risks and benefits of the research; may impact subject safety, affect the integrity of research data and/or affect a subject's willingness to participate in the research. Deviations that place a subject at risk, but do not result in harm are considered to be major deviations.

Minor Deviation: A deviation or violation that does not impact subject safety, compromise the integrity of research data and/or affect a subject's willingness to participate in the research.

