9.2 Event Documentation

Participants will be monitored for adverse events from the 1st dose of study treatment through day 12. After that time point, events meeting the definition of serious and at least possibly related to study treatment will be documented upon knowledge.

We will collect the following Grade 2-5 adverse events attributable to AC:

Aspiration of activated charcoal

In addition any event meeting the definition of a serious adverse event (SAE) regardless of attribution that occurs during this period will be documented in the source document and recorded in OnCore.

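### Item 2 of the volunteer rating form asks only for issues the volunteer thinks are charcoal-related, which does not fit the protocol's own adverse event definition or its attribution rule

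*Combined protocol and SAP*

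**What the plan says.** The rating form in Appendix II has two items. Item 1 is the 5-point rating. Item 2 is the only event question on the form: "Have you had any issues since last drink of charcoal that you think may be related to your charcoal experience". Section 6.1.3 has volunteers rate daily from day 1 through day 12.

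Section 9.1 defines an adverse event as "Any untoward medical occurrence associated with the use of a drug in humans, whether or not considered drug related". On causality it says: "Attribution must be assigned by the treating physician or the PI".

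Staff also look for events by other routes. Under Section 6.2, for 2 days after each round, "a member of the study team will contact the subject and screen for all grade 2 or higher AEs and SAEs". The Section 7 schedule lists "Screen for AEs" on Monday, Tuesday and Wednesday, in a different row from the rating, and "Telephone call from study staff to check for AEs" on Thursday and Friday.

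The secondary endpoint (Section 11.2) is the incidence of AEs of grade 2 and above that are judged at least probably related to AC by day 12.

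**The concern.** Relatedness is meant to be judged after an event has been reported, by someone qualified to judge it. Item 2 reverses that order on the form. A volunteer who puts a stomach complaint down to lunch or stress can truthfully answer no, and the form then gives the physician nothing to attribute.

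What is at stake is the secondary safety endpoint. It counts events by the physician's or PI's judgement, so it is only as complete as the set of events that reach them. An event lost because the volunteer judged it unrelated cannot be recovered by a later, better judgement.

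**Working it through.** No formula applies, and the plan states no figure that depends on this wording. The check is to set the provisions side by side.

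| Source | Days | Limited by the volunteer's view of cause? | Grade limit | Wording given? |
|---|---|---|---|---|
| Form, item 2 (Appendix II) | Daily, days 1–12 (6.1.3); rating listed M/T/W only in Section 7 | Yes | None | Yes |
| AE screen (Section 7) | M/T/W | No | None stated | No |
| Call or contact (Sections 6.2 and 7) | Th/F | No | Grade 2 or higher in 6.2; none stated in Section 7 | No |
| SAE documentation (Section 9.2) | First dose to day 12 | No | Serious events | Not applicable |

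1. **Definition.** Section 9.1 includes events whether or not they are thought related. Item 2 leaves out those the volunteer thinks unrelated. The two do not match.
2. **Who judges.** Section 9.1 gives attribution to the treating physician or the PI. Item 2 asks the volunteer to make a first cut. Section 9.2 does restrict non-serious collection ("We will collect the following Grade 2-5 adverse events attributable to AC"), but under 9.1 that attribution still belongs to the physician or PI, so the event has to reach them first.
3. **What else catches the event.** The staff screens and calls have no relatedness filter, and the Section 6.2 contact uses the same grade threshold as the endpoint. They cover much of what item 2 could miss.
4. **What stays open.** The M/T/W screen has no stated question or instrument. It falls on the same days as the rating, and item 2 is the only event question whose words are given. If item 2 served as that screen in practice, the filter would apply on all 6 drinking days. The documents do not say that it does, nor that it does not.
5. **Days without staff contact.** Section 6.5 gives 12 days, of which 6 are active and 4 are follow-up: 12 − 6 − 4 = 2 days (the weekend between rounds). If the form is completed daily as Section 6.1.3 says, it is the only prompt on those 2 days, although the next Monday's screen can still pick up what was missed.
6. **Scale of a single miss.** If incidence is counted per volunteer (an assumption, since 11.2 does not say), one volunteer whose only event goes unrecorded moves it by 1/12, about 8 percentage points. This is the weight of one miss, not an estimate of how many occur.

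**The case against.** The strongest reply is that this is a product rating form, not the AE source. Section 6.1.3 refers to an appendix form only for the rating, Section 9 places routine AE documentation in the OnCore AE form, and Section 3 assigns tolerability to staff contact after each round. On that view a loosely worded item on a rating sheet contradicts nothing. Much of this stands, and it keeps the point small. It does not remove the mismatch: the item asks about events, its answers will be read as event information, and nothing says they are not to be used that way.

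Four stronger readings are tempting, but the documents do not support them.

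- **The volunteer screens all events before a physician sees them.** This is true of the form only. The Section 6.2 and Section 7 routes have no such filter, and Section 9.2 documents SAEs regardless of attribution.
- **Milder symptoms have only this form.** The Section 7 screens and calls state no grade limit, and grade 1 events are outside the endpoint in any case.
- **The wording favours apple juice over water, because juice offers a second explanation.** Both criteria in Section 12.3, the average score and the share of low ratings, come from item 1. Section 11.2 specifies no comparison between liquids, and a volunteer may well take the charcoal experience to mean the whole drink. Any reporting fraction by liquid would be invented.
- **Relatedness should be to AC and its liquid together.** Section 9 says that study drug "refers to study product, medical grade Oral AC", and Sections 1.2, 9.2 and 11.2 also tie relatedness to AC. That is a coherent choice. Changing it would be a separate design preference.

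**Conclusion.** The point holds for the form. Item 2 does not fit the Section 9.1 definition or its attribution rule, and an event that a physician would have judged probably related may go unprompted there. The staff screens and calls limit the consequence for the secondary endpoint. How far they do so depends on what is actually asked on M/T/W, which the plan leaves open.

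The size of the loss cannot be estimated from the documents. It does not touch the selection of the combination under Section 12.3. This is an inexpensive improvement in safety capture, not a threat to the study's main result.

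**What to change.** Reword item 2 so that it does not ask about cause, for example: *Have you had any new or worse symptom since your last drink, whatever you think caused it? If yes, what and when did it start?* Use the same neutral question for the M/T/W AE screen and say so in Section 7 or 9.2. Leave attribution to the treating physician or the PI as Section 9.1 already requires. Sections 9.1 and 11.2 need no change.

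The cost is a one-line form revision and a sentence in the protocol. The downside is a few more unrelated complaints to grade among 12 volunteers.
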